7. EFFICACY ANALYSIS

7.1 Primary Efficacy Endpoint and Analysis

The primary endpoints of this study are safety related and therefore there are no primary efficacy endpoints.

7.2 Secondary Analysis

A secondary analysis of efficacy to evaluate response to MT-3724 in combination with lenalidomide will be performed in this trial. The efficacy parameters of interest are objective response rate (ORR), best objective response rate (BORR), and duration of response (DOR). All efficacy summaries will be based on the safety population.

6.1.1 Objective Response Rate

The ORR measures the proportion of subjects with a reduction in tumor size (Partial Response or Complete Response) using the five-point scale (5PS) per the Lugano Classification for Lymphoma (2) adjusted according to LYRIC (lymphoma response to immunomodulatory therapy criteria) (3). An overview of LYRIC is presented in the protocol. The proportion of subjects with a Partial Response or Complete Response will be summarized and presented at each scheduled visit. The ORR representing clinically significant clinical benefit in this study will comprise the Lugano Score 1, 2 or 3, or the CR, CRu or PR. The number and percentage of subjects with clinically significant results will be presented.

6.1.2 Best Objective Response Rate

The best ORR (BORR) at all time points will be reported. Subjects who experience disease progression before undergoing the first tumor assessment will be added to the disease progression stratum. The BORR will be descriptively summarized by the treatment group / cohort; the exact 95% confidence intervals will also be produced.

6.1.3 Duration of Response

All subjects achieving clinically significant clinical benefit according to the response criteria (CR, CRu, PR, or stable disease for at least 3 months) will be included in the analysis of the duration of tumor response (DOR).

DoR is defined as the time interval (days) from date of the first objective response (CR, CRu, or PR; achieved after the date of exposure to MT-3724) to the date of disease progression.

Duration of Response (days) =

Date of Progression after 1st Objective Response – Date of 1st Objective Response + 1

- If the subject does not have a response of CR, CRu, or PR the Duration of Response will be set to missing.
- Subjects not meeting the criteria for progression or death by the analysis cutoff date will be censored at their last evaluable disease assessment date and their first response will be noted as ongoing.
- For death or PD after more than 1 missed evaluation, the duration will be censored at the last visit.

The DOR will be descriptively summarized by the treatment group / cohort; the exact 95% confidence intervals will also be produced.

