7.9 Efficacy analyses

The statistical analysis of efficacy variables will be performed on the safety population.

Tumor assessment will be performed by the FDG-PET-CT scan in subjects with FDG-avid NHL histology along with CT or MRI to capture measurements, wherever possible, and by the CT or MRI scan in subjects with low or variable FDG avidity. The investigator at each site will determine the ORR at each time point based on the radiologist's measurement of all evaluable lesions.

The investigator at each site will determine the objective tumor response (OR) using the 5PS per the Lugano Classification for Lymphoma ([Cheson 2014](#)) adjusted according to LYRIC (lymphoma response to immunomodulatory therapy criteria) ([Cheson 2016](#)). An overview of LYRIC is presented in [Appendix 3](#). The BORR of all time points will be reported. Subjects

who experience disease progression before undergoing the first tumor assessment will be added to the disease progression stratum. The BORR will be descriptively summarized by the treatment group/cohort; the exact 95% confidence intervals will also be produced.

The ORR representing clinically significant clinical benefit in this study will comprise the Lugano Score 1, 2 or 3, or the CR or PR. All subjects achieving clinically significant clinical benefit according to both response criteria will be included in the analysis of the DOR. DOR is defined as the time from the first documented complete or partial response to the actual date of disease progression or death before progression. The PFS will be defined as the time from the start of treatment with MT-3724 on C1D1 to the date of disease progression or death from any cause. Subjects who have not progressed or died at the time of data base lock will be censored at the date of their last tumor assessment. The DOR will be descriptively summarized by the treatment group/cohort; the exact 95% confidence intervals will also be produced.

The DCR will be defined as the percent of subjects with objective response of CR, PR or stable disease (SD, defined as SD for 6 months or longer). The DCR will be analyzed using similar methods as the ORR. Further details will be provided in the SAP.

A detailed description of analysis methods will be provided in the SAP to be completed before the EoT Visit in the last subject.

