Response and Site	PET-CT-Based Response	CT/MRI-Based Response
Complete	Complete metabolic response	Complete radiologic response (all of the following)
Lymph nodes and extralymphatic sites	5PS score of 1, 2, or 3 ¹ with or without residual mass. It is recognized that in Waldeyer's ring or extranodal sites with high physiologic uptake or with activation within spleen or marrow (e.g., with chemotherapy or myeloid colony-stimulating factors), uptake may be greater than normal mediastinum and/or liver. In this circumstance, complete metabolic response may be inferred if uptake at sites of initial involvement is no greater than surrounding normal tissue even if the tissue has high physiologic uptake	Target nodes/nodal masses must regress to ≤ 1.5 cm in LD _i No extralymphatic sites of disease
Nonmeasured lesion	Not applicable	Absent
Organ enlargement	Not applicable	Regress to normal
New lesion(s)	None	None
Bone Marrow	No evidence of FDG-avid disease in marrow	Normal by morphology; if indeterminate, IHC negative
Partial	Partial metabolic response	Partial remission (all of the following)
Lymph nodes and extralymphatic sites	Score 4 or 5 on the 5PS (Table 13) with reduced uptake compared with baseline and residual mass(es) of any size. At interim, these findings suggest responding disease. At end of treatment, these findings indicate residual disease	$\geq 50\%$ decrease in SPD of up to 6 target measurable nodes and extranodal sites When a lesion is too small to measure on CT, assign 5 mm x 5 mm as the default value When no longer visible, 0 x 0 mm For a node >5 mm x 5 mm, but smaller than normal, use actual measurement for calculation
Nonmeasured lesion	Not applicable	Absent/normal, regressed, but no increase
Organ enlargement	Not applicable	Spleen must have regressed by $>50\%$ in length beyond normal
New lesion(s)	None	None

Bone Marrow	Residual uptake higher than uptake in normal marrow but reduced compared with baseline (diffuse uptake compatible with reactive changes from chemotherapy allowed). If there are persistent focal changes in the marrow in the context of a nodal response, consideration should be given to further evaluation with MRI or biopsy or an interval scan	Not applicable
No response or stable disease	No metabolic response	Stable disease

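### SAP 6.1.3 contradicts itself and protocol 7.9 on who enters the duration-of-response analysis and whether death ends a response, and it names no estimator for censored durations, so DOR is not reproducible as written

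*SAP*

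**What the plan says.** **SAP 6.1.3** (printed under section 7.2, Secondary Analysis):

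- Population: "CR, CRu, PR, or stable disease for at least 3 months) will be included in the analysis of the duration of tumor response (DOR".
- Subjects without an objective response: "If the subject does not have a response of CR, CRu, or PR the Duration of Response will be set to missing".
- Formula: "Date of Progression after 1st Objective Response – Date of 1st Objective Response + 1". The sentence defining DOR likewise ends at progression.
- Censoring: "Subjects not meeting the criteria for progression or death by the analysis cutoff date will be censored at their last evaluable disease assessment date". A further rule covers death or progression after more than one missed evaluation and censors it at the last visit.
- Summary: "The DOR will be descriptively summarized by the treatment group / cohort; the exact 95% confidence intervals will also be produced". SAP 6.1.2 uses the same wording for the best response rate, which is a proportion.

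SAP 6.1.4 specifies Kaplan-Meier percentiles with 95% confidence intervals for PFS. Section 6.1.3 has no such statement for DOR.

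**Protocol 7.9** (and the synopsis) sets a different population: "All subjects achieving clinically significant clinical benefit according to both response criteria will be included in the analysis of the DOR". DOR runs from the first CR or PR "to the actual date of disease progression or death before progression". The sentence before the population rule gives clinical benefit as a Lugano score of 1 to 3, *or* CR or PR. Appendix 3, Table 12 describes a PET-based partial response as "Score 4 or 5 on the 5PS (Table 13) with reduced uptake compared with baseline and residual mass(es) of any size". Its response categories do not include CRu.

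SAP section 4 says that the SAP's methods take precedence over the protocol.

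**The concern.** DOR is a named secondary endpoint in the protocol and one of three efficacy parameters of interest in SAP 7.2. Protocol 1.5 presents the regimen as replacing rituximab in the R² combination, and section 1.3.1 quotes a median DOR of 10.2 months for R². No formal comparison is planned, but readers will probably set the two figures side by side.

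Two programmers working from SAP 6.1.3 could differ on three things: the denominator, the treatment of deaths, and whether the median is a Kaplan-Meier estimate or the middle of a list of partly censored times. With few responders, each choice can move the reported median by months. The study is open-label, so a choice left until analysis would be made with the data in view.

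**Working it through.** The documents state no expected DOR, event count or precision, so there is no planned figure to reproduce. The check compares the rules and then sizes the two open choices.

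**1. Population.** A subject with stable disease only is admitted by the population sentence and then given a missing DOR. No stable-disease duration can enter the result. What becomes ambiguous is N and any percentage based on it.

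**2. End event.** Take a responder who dies without progression, having missed no more than one evaluation.

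- Formula: there is no progression date, so no value.
- Cutoff censoring rule: it covers subjects with neither progression nor death, so it does not apply.
- Gap rule: it needs more than one missed evaluation, so it does not apply.

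No SAP rule gives this subject a duration. Protocol 7.9 counts the death as the end of response.

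**3. Gap rule.** Protocol 6.6 schedules scans every second 28-day cycle (2 × 28 = 56 days), while clinic visits are more frequent. Protocol 3.5 makes long-term follow-up visits telephone calls. With exactly two missed scans on that schedule, an event can come up to 3 × 56 = 168 days after the last evaluable scan. Censoring at the last visit could credit most of that interval as response without a scan to support it.

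**4. Protocol population.** If the phrase about both criteria means a score of 1 to 3 together with CR or PR, a PET-based PR, which scores 4 or 5, cannot qualify.

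**5. Size if a plain median is used.** Assumptions: exponential DOR with true median m = 10.2 months (the R² figure in protocol 1.3.1, not a planning value of this trial), and follow-up uniform between a and b months, which the documents do not give. The hazard is λ = ln 2 / 10.2 = 0.0680 per month. In large samples the plain median, with censored times taken as observed, solves

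exp(−λt) × G(t) = 0.5, where G(t) = 1 for t < a and (b − t)/(b − a) for a ≤ t ≤ b.

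| Follow-up (months) | Plain median | Kaplan-Meier target |
|---|---|---|
| 4 to 20 | 7.1 | 10.2 |
| 6 to 24 | 8.2 | 10.2 |
| 12 to 30 | 10.2 | 10.2 |
| 18 to 36 | 10.2 | 10.2 |

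Check of the first row: exp(−0.0680 × 7.1) = 0.617, G = (20 − 7.1)/16 = 0.806, and the product is 0.50. Under this model the bias disappears once minimum follow-up reaches the true median.

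**6. Size if deaths are censored.** Let f be the share of events that are deaths without progression, with constant hazards. Censoring those deaths leaves a hazard of (1 − f)λ, so the Kaplan-Meier median becomes m/(1 − f):

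- f = 5%: 10.2/0.95 = 10.7 months
- f = 10%: 10.2/0.90 = 11.3 months
- f = 20%: 10.2/0.80 = 12.75 months
- f = 30%: 10.2/0.70 = 14.6 months

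**The case against.** The other side has several fair points.

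- **Stable disease.** A reader might infer that stable-disease durations will be mixed into DOR. They cannot be: the set-to-missing rule keeps them out. This point stands, and only the count is affected.
- **Deaths.** A reader might infer that deaths are simply excluded, or that only progressors are summarized. Both censoring rules mention death, and subjects still in response are censored rather than dropped. The text is contradictory; it does not clearly exclude deaths.
- **The phrase about both criteria.** A reader might infer that every metabolic PR is lost. That is one reading of protocol wording. It could also mean Lugano and LYRIC, or the PET and CT columns of Table 12. The SAP does not repeat the phrase and claims precedence. This point stands, though the protocol wording still needs correcting.
- **Estimator.** A descriptive summary does not rule out Kaplan-Meier, and an exact order-statistic interval exists for an uncensored median. That removes any claim that DOR will be biased. It leaves the estimator and interval method unstated for data the SAP itself censors.
- **Follow-up and noise.** Protocol 3.5 has responders followed radiologically for up to 18 months after the last MT-3724 dose, so a plain median may show little bias. Sampling error is also large: simulating 14 responders with 4 to 20 months of follow-up, the Kaplan-Meier median is not reached in about 15% of trials and its quartiles run from about 7 to 14 months. Both points limit the practical effect. Neither supplies the missing rules.

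The precedence clause does not help, because it makes the progression-only formula govern and leaves the SAP's internal conflicts in place.

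**Conclusion.** SAP 6.1.3 is internally inconsistent on stable disease and death, conflicts with protocol 7.9 on the end event and the population, uses an undefined category (CRu), censors late events at a date that need not have a scan, and names no censored-data estimator. DOR cannot be reproduced from it.

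Bias is possible in either direction but not established. For an assumed true median of 10.2 months, a plain median falls between about 7 and 10.2 months across the follow-up patterns shown. Censoring deaths raises the median to between 10.7 and 14.6 months for death shares of 5% to 30%. These figures rest on exponential durations and on assumed follow-up and death shares; they illustrate the effect and do not predict this trial's result. A longer true median would need longer minimum follow-up before the plain median became safe.

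This is a should-fix: DOR is a secondary endpoint in a descriptive study without a power calculation, and dose decisions, sample size and the primary safety analysis do not depend on it.

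**What to change.** Use one definition in both documents.

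1. **Population:** subjects with CR or PR. Delete stable disease and CRu from SAP 6.1.3, and replace the protocol phrase about both response criteria (7.9 and synopsis).
2. **Duration:** first CR or PR to the earlier of progression by Lugano/LYRIC or death, in both the SAP text and the formula. Name the criteria explicitly, since SAP 6.1.4 cites RECIST for PFS.
3. **Censoring:** at the last evaluable tumor assessment, including the last one before a gap of more than one missed evaluation.
4. **Estimation:** Kaplan-Meier median and quartiles with a stated 95% confidence interval method, as for PFS. Keep exact intervals for response rates.

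The cost is SAP wording and programming and one corrected protocol phrase. No new data are needed. The change should be made before the durations are analysed.

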5. GENERAL CONSIDERATIONS FOR DATA ANALYSIS

Quantitative data will be described by the following summary statistics: arithmetic mean, standard deviation, median, minimum, and maximum. Where appropriate, descriptive summary statistics will be tabulated for the absolute values and changes from baseline. Graphical illustrations will be provided where appropriate. Qualitative data will be presented in the frequency tables.

Analyses will be performed using SAS for Windows statistical software, version 9.2 or higher (SAS, Cary, NC), except where other software may be deemed more appropriate.

CTI Clinical Trial and Consulting Services (Cincinnati, OH) will perform all efficacy and safety statistical analyses.

Subject data will be listed, sorted by cohort and subject number. Dose escalation cohorts and MTD expansion cohort will be reported separately and combined at the recommended phase 2 dose.

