6.1.4 Progression-free Survival

Progression-free survival (PFS) is the time from study drug administration until disease progression or death. The disease assessment by the RECIST V1.1 criteria occurs at Screening, months 1, 3, 6, 9, 12, 18 and 24.

PFS is defined as the interval between the date of first infusion of and the date of PD or death, whichever is first reported.

PFS (days) =

Date of Progression – Date of 1st Infusion + 1

The following Kaplan-Meier (KM) estimates will be provided:

- 25th, 50th (i.e., median) and 75th KM percentiles with 95% CIs
- Number and percent of subjects censored/not censored

KM estimates of the proportion of subjects event-free at: 3, 6, 12, 18, and 24 months (note: not all estimates may be provided for interim analyses)

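### SAP 6.1.3 censors duration of response but names no estimator that handles censoring and no parameter for its interval, so the summary could be biased low

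*SAP*

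**What the plan says.** DOR is listed under the tumor-response secondary objective (Protocol 2.2) and among the efficacy parameters of SAP 7.2. SAP 6.1.3 sets two censoring rules. For ongoing responses: "Subjects not meeting the criteria for progression or death by the analysis cutoff date will be censored at their last evaluable disease assessment date". For events found late: "For death or PD after more than 1 missed evaluation, the duration will be censored at the last visit". The analysis sentence that follows is "The DOR will be descriptively summarized by the treatment group / cohort; the exact 95% confidence intervals will also be produced". Protocol 7.9 has the same sentence: "The DOR will be descriptively summarized by the treatment group/cohort; the exact 95% confidence intervals will also be produced".

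Three neighbouring passages matter:

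- SAP 5, the general rule: "Quantitative data will be described by the following summary statistics: arithmetic mean, standard deviation, median, minimum, and maximum".
- SAP 6.1.2, for best response, which is a proportion: "The BORR will be descriptively summarized by the treatment group / cohort; the exact 95% confidence intervals will also be produced". The DOR sentence is this one with the endpoint changed.
- SAP 6.1.4, for PFS: "The following Kaplan-Meier (KM) estimates will be provided", starting with "25th, 50th (i.e., median) and 75th KM percentiles with 95% CIs".

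SAP 4 states that the SAP's methods override the protocol's. Neither document says how a censored duration enters the DOR summary.

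**The concern.** A censored duration is a lower bound, not a measurement. The statistics in SAP 5 have no way to use that information: a programmer must either treat the censoring time as the end of response or leave the subject out. The exact interval is a standard choice for a response rate, but for DOR the plan does not say whether it is for a mean, a median or a proportion. Two programmers could follow 6.1.3 faithfully and report medians several months apart. The figure would then depend partly on how long responders happened to be followed, so cohorts with shorter follow-up could look worse for that reason alone.

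**Working it through.** The plan gives no DOR estimate, event count or precision, so there is no figure to reproduce. I checked how far each literal reading could miss.

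**Inputs**

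- Responders: Part 2 enrols up to 40 (Protocol 3.7). Applying the 33% ORR quoted for lenalidomide-rituximab in Protocol 1.3.1 gives 0.33 × 40 = 13.2, taken as 13. This is an assumption.
- True median DOR: 10.2 months, from the same paragraph, with an exponential shape. This is an assumption.
- Follow-up after first response: uniform over the windows below. These are assumptions; the documents give no such windows.

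**Formula.** Let T be the true duration, C the follow-up and X = min(T, C) the recorded time. Then P(X > m) = S(m) × G(m), with S(m) = exp(−λm), λ = ln 2 / 10.2 = 0.0680 per month, and G(m) = (b − m)/(b − a) for a < m < b when C is uniform on (a, b). In large samples the ordinary median of X solves S(m) × G(m) = 0.5.

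For follow-up of 3-18 months, try m = 6.4: S = exp(−0.0680 × 6.4) = 0.647, G = (18 − 6.4)/15 = 0.773, product 0.50. The ordinary median is therefore about 6.4 months. If nobody is censored before 10.2 months, G(10.2) = 1 and the solution is 10.2: no bias.

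**Results** (median DOR in months; simulated with 13 responders, at least 4,000 trials per window)

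| Follow-up | Censored | Ordinary median, large sample | Ordinary median, 13 responders | Censored dropped | Kaplan-Meier | KM median not reached |
|---|---|---|---|---|---|---|
| 2-14 | 60% | 5.4 | 5.5 | 3.5 | 10.5 | 40% |
| 3-18 | 51% | 6.4 | 6.6 | 4.2 | 10.1-10.3 | 22% |
| 6-24 | 38% | 8.2 | 8.3 | 5.5 | 10.3 | 8% |
| 12-30 | 25% | 10.2 | 10.2 | 6.9 | 10.2 | 2% |
| 18-30 | 20% | 10.2 | 10.2 | 7.5 | 10.2 | under 1% |

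The first three 13-responder ordinary medians are averages over trials; the other 13-responder entries are medians over trials. Unrounded, the three are 5.49, 6.56 and 8.34, which are 46%, 36% and 18% below 10.2.

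**Mean.** The true mean is 10.2 / ln 2 = 14.7 months. The ordinary mean of X is low in every row, from 5.9 months (2-14) to 11.7 (18-30), because min(T, C) can never exceed T. With censored responders dropped it is lower still.

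**Early censoring within long follow-up.** With 18-30 months' follow-up, adding 20% or 40% per year of early censoring (for example for new therapy) brings the ordinary median to 8.0 or 6.3 months. Kaplan-Meier stays at 10.1 to 10.2, given that the simulated censoring is unrelated to outcome.

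**Interval.** An exact order-statistic interval for a median does exist. With 13 values, the 3rd to 11th has nominal coverage 97.8%. Applied to times that ignore censoring, it covers the true median 97.9% of the time with 18-30 months' follow-up, but 76% (0-24), 56% (0-18) and 50% (3-15). It also needs at least six values for 95%: five give 1 − 2 × 0.5^5 = 93.75%, six give 1 − 2 × 0.5^6 = 96.9%.

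**The case against.** The best defence is that 6.1.3 is incomplete rather than wrong. It does not name the mean or the median, and it does not say censored times count as completed durations. Setting censoring rules, and flagging censored responses as ongoing, suggests a time-to-event analysis was intended; SAP 5 is only a general default. Subjects may be treated until progression and are followed for 18 months after the last MT-3724 dose (Protocol 3.5), and the SAP describes analyses after the trial is complete (SAP 1). With follow-up that long the ordinary median can be right, as the last two rows show. Kaplan-Meier is no cure for sparse data either: its median is often not reached in the shorter windows. Part 1 cohorts of 3 to 6 subjects would yield about one or two responders each at a 33% response rate. Finally, the study is descriptive and unpowered, and dose decisions rest on DLTs.

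Much of this stands. It makes the bias conditional and lowers the priority. It does not remove the gap. The next subsection spells out Kaplan-Meier for PFS, and DOR gets none of it. Nothing secures follow-up beyond the median: imaging follow-up ends at new anticancer treatment, long-term visits are telephone calls with scans taken from medical records (Protocol 3.5), late events are censored, and informal analyses may be run at any time (SAP 9). Long follow-up also does not help the mean, or either statistic if censored responders are dropped.

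**Conclusion.** The DOR analysis is under-specified in a way that permits a materially wrong summary. Entering censored times as observed biases the mean low, and the median too when censoring precedes the true median. Dropping censored responders biases both low. On the assumptions above, the ordinary median is short by about 18% to 46% for follow-up of 6-24 down to 2-14 months, and by nothing material for 12-30 months or longer. Those sizes rest on an exponential shape, a 10.2-month median and chosen follow-up windows.

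A reader might infer three stronger things that the documents do not support:

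- That the reported median is bound to be low. It need not be, if follow-up is long and censored times are kept.
- That an exact interval for DOR cannot mean anything. The supportable statement is that the plan defines none, and that the order-statistic version fails under early censoring.
- That the result could not be compared with censoring-adjusted published medians. Protocol 1.3.1 does not say how the medians it quotes were estimated, and no such comparison is planned.

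Priority: should-fix. DOR is a descriptive secondary endpoint with no test or decision rule attached.

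**What to change.** In SAP 6.1.3, replace the last sentence with:

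> DOR will be estimated by Kaplan-Meier among subjects with an objective response (CR, CRu or PR, as defined in this section): median and quartiles with 95% CI (Brookmeyer-Crowley, log-log), proportion still in response at 6 and 12 months, and number censored.

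Keep exact (Clopper-Pearson) intervals for response rates; for 13 of 40, for example, the interval is 18.6% to 49.1%. For Part 1 cohorts with one or two responders, list individual durations with a censoring flag instead of a median.

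Because the SAP takes precedence, this edit is enough for the analysis; align Protocol 7.9 and the synopsis at the next amendment. Whether death counts as a DOR event also needs settling: Protocol 7.9 includes it, while the SAP formula uses the progression date only. That is a separate point.

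The cost is one sentence, using a method the SAP already specifies for PFS. The downside is that the median may be reported as not reached when data are immature, in about 8% to 40% of simulated trials in the three shorter windows. That is an honest description of such data, and the 6- and 12-month proportions can still be given where follow-up reaches those times.
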